**5.3.3.1 Primary analysis methods**

The efficacy and safety information recorded on CRF will be summarized by tables presented in frequency and percentage for categorical variables, in mean with SD as well as median with the minimum and maximum for continuous variables. The comparison between three groups will be analyzed by nonparametric method as appropriate. All adverse events will be summarized with coding term, severity, relationship to study drug by frequency tables with the counts and percentage. In addition, serious adverse events will be listed with event narration.

**5.3.4 Determination of sample size**

In part I, six subjects each will be evaluated for safety and efficacy assessments at 1 or 2 capsules TID dose for 28 days, sequentially.

**CONFIDENTIAL**

Project No. BLI-1005-002

Statistical Analysis Plan for PDC-1421

“Final” Page 19 of 34

Protocol Version: 2.3

SAP Version: 20180626\_01

In part II, this is a small proof-of-concept study to evaluate 2 doses of PDC-1421 and placebo in the treatment of major depressive disorder. Based on our study design, it is planned to enroll 60 subjects who met the intent-to-treat (ITT) basis.

#### **5.4 Changes in the Conduct of the Study or Planned Analyses**

All the statistical analysis will follow protocolized statistical contents.

## 6. STATISTICAL EVALUATIONS

The statistical objective of this study is to assess the safety and efficacy profiles in three groups - 1 PDC-1421 capsule plus 1 placebo, 2 PDC-1421 Capsule, and 2 placebos.

### 6.1 Data Sets Analyzed

Two study populations are intention-to-treat (ITT) population and per-protocol (PP) populations which are defined in section 5.3.1.

The efficacy evaluations will be performed on both of the ITT and PP datasets while the safety evaluations will be performed on the ITT dataset. The primary conclusion will be made for the primary endpoint on the ITT population

Demographic and baseline (Visit 2) characteristics will be performed on the ITT population.

Sample size, mean, 95% confidence interval of mean, median, standard deviation, inter-quartile range, maximum and minimum will be summarized for continuous variables. For categorical variables, the frequency and percentage will be provided.

### 6.2 Demographics and Other Baseline Characteristics

Demography and baseline characteristics will be summarized in descriptive statistics and listed by part, center and treatment.

#### 6.2.1 *Demographic data*

Demographic variables including age(year), height (cm), weight (kg) and BMI (kg/m^2) will be summarized. Subjects' gender will be tabulated.

Age (years) = integer of (date of initial visit – date of birth) / 365.25

BMI (Kg/m^2) = (weight) / (height) rounds to one decimal place

#### 6.2.2 *Major Depressive Disorder History and Medical history*

Frequency table of Diagnosis and Statistical Manual of Mental Disorders-IV, text revision (DSM-IV-TR) will be presented.

Frequency table of subject with medical history and current medical condition will be presented.

**CONFIDENTIAL**

Project No. BLI-1005-002

Statistical Analysis Plan for PDC-1421

“Final” Page 21 of 34

Protocol Version: 2.3

SAP Version: 20180626\_01

General medical history will be presented in incidence table and listed for each subject.

Ongoing medical conditions will be presented separately from the cured diseases.

### **6.2.3 Concomitant medications**

Frequency table of subjects with pre-treatment and concomitant medications will be presented. WHO Drug Dictionary will be applied.

Pre-treatment medications are the medications taken before the first dosing of study drug, while concomitant medications are those taken during the treatment duration (from first dosing date of study drug to the day before exiting from study).

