5.2.3 Part II.- Treatment Period (Visit 2~5) and Follow-up (Visit 6)

Laboratory data and results of other tests and evaluation shall be obtained at screening to determine the appropriateness of subject enrolled in this study. Subjects who meet the eligibility criteria will be enrolled and take study drugs. Baseline data (Visit 2), including physical examination, vital sign, ECG, hematology, blood chemistry, HAM-D-17, CGI, HAM-A, MADRS, DSSS, C-SSRS and concomitant medication evaluation, will be collected before dosing study drug. At visits 2, 3 and 4 (weeks 0, 2 and 4), each subject will be dispensed a supply of study drug sufficient for 2-week treatment period. The subjects will be instructed to take one dose (i.e., two capsules) after a meal thrice daily for every week. Subjects will be assessed every two weeks and receive the study drug for next two weeks till the end of trial. At visits 2, 3, 4 and 5, the safety and efficacy parameters will be evaluated by the following items.

- Physical examination: skin, head, neck, eyes, ears, nose, throat, heart, lungs, abdomen (liver, spleen), neurological examination, lymph node and extremities.
- Vital sign: heart rate, blood pressure, body temperature
- ECG
- Hematology: RBC, WBC, platelets, hematocrit, hemoglobin, prothrombin time (PT), partial thromboplastin time (aPTT). If the interval of visit 1 and visit 2 is within 7 days, Hematology test of visit 2 can be skipped.
- Blood chemistry: AST, ALT, LDH, total bilirubin, BUN, serum creatinine, free thyroxine (FT4), TSH, sodium, calcium, potassium, LDL, HDL, triglyceride, cholesterol. If the interval of visit 1 and visit 2 is within 7 days, Blood chemistry test of visit 2 can be skipped.
- HAM-D-17, CGI, HAM-A, DSSS, MADRS, C-SSRS and concomitant medication evaluation.
- AE/SAE evaluation
- Drug accountability

Follow-up visit will be performed at visit 6 after one week of the last dose administration.

The test items are outlined in the following:

- Physical examination: skin, head, neck, eyes, ears, nose, throat, heart, lungs, abdomen (liver, spleen), neurological examination, lymph node and extremities.
- Vital sign: heart rate, blood pressure, body temperature
- ECG
- Hematology: RBC, WBC, platelets, hematocrit, hemoglobin, prothrombin time (PT), partial thromboplastin time (aPTT)
- Blood chemistry: AST, ALT, LDH, total bilirubin, BUN, serum creatinine, free thyroxine (FT4), TSH, sodium, calcium, potassium, LDL, HDL, triglyceride, cholesterol.

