- HAM-D-17, MADRS, DSSS, CGI, HAM-A and C-SSRS and concomitant medication evaluation.
- Pregnancy test
- AE/SAE evaluation

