5.3 Other Medication During the Study

To avoid conflict or unknown effects with the study drug, subjects are prohibited from taking any antidepressants and psychoactive drugs, as per the exclusion criteria, including MAOIs (monoamine oxidase inhibitor), NRIs (norepinephrine reuptake inhibitor) and norepinephrine receptor agonist/antagonist. Subjects can't combine the newly-initiated psychotherapy. If subjects have severe insomnia, Zolpidem, Zopiclone or Zaleplon can be used in four nights per week from V1 to the first week after V2. (The maximum daily dose in Zolpidem, Zopiclone and Zaleplon are 10 mg, 7.5 mg and 10 mg respectively.)

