#### Part II.

### 5.2.2 *Study Medication Administration*

In part I, six subjects each will take 1 or 2 capsules thrice daily for 28 days, sequentially. Subjects are assessed twice in the first week after drug administration and they will receive the study drug bag for the following 7 days every week. In part II, eligible subjects are randomized into one of three treatment arms in a 1:1:1 ratio (one capsule of PDC-1421 Capsule and placebo thrice daily; two capsules of PDC-1421 Capsule thrice daily; two capsules of placebo thrice daily) for 42 days. After the two weeks of drug administration, subjects will return to the center for assessments then get another study drug bag for the following 14 days. The biweekly clinic visits are three times and one week later after the last dose for follow-up.

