## 5.3 Statistical Methods Planned in the Protocol and Determination of Sample Size

### 5.3.1 Populations for analysis

The efficacy measures are conducted on the per-protocol (PP) and intent-to-treat (ITT) basis. The per protocol will be defined as (1) The drug compliance is at least 80% (2) Subjects have completed data to determine the primary endpoint. (3) Subjects cannot have protocol deviation. The protocol deviation will be defined as (1) Inclusion or exclusion criteria not satisfied. (2) Not permitted concomitant medications (3) Wrong randomized treatment prescribed. An intent-to-treat (ITT) basis will be defined as the data are analyzed by the treatment groups to which the randomized patients who take at least one dose of study medication and have any post-baseline safety data collected.

The safety measures are conducted on the ITT basis.

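### Read literally, the per-protocol rule lets a prohibited drug started after the week-6 rating remove a compliant patient from the supportive week-6 MADRS analysis

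*SAP*

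**What the plan says.** The point comes from reading five places together.

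- **PP rule (SAP 5.3.1, repeating protocol 8.3).** Besides 80% compliance and complete primary-endpoint data, the rule requires "3) Subjects cannot have protocol deviation". The list of deviations includes "2) Not permitted concomitant medications (3) Wrong randomized treatment prescribed". No date limit is attached.
- **Meaning of concomitant (SAP 6.2.3).** The only definition in the SAP is that "concomitant medications are those taken during the treatment duration (from first dosing date of study drug to the day before exiting from study".
- **The ban (protocol 5.3).** Here "subjects are prohibited from taking any antidepressants and psychoactive drugs, as per the exclusion criteria". The section title covers the whole study, and no end date is given.
- **Follow-up (protocol 5.2.3).** "Follow-up visit will be performed at visit 6 after one week of the last dose administration". The items collected there are "HAM-D-17, MADRS, DSSS, CGI, HAM-A and C-SSRS and concomitant medication evaluation", so a drug started in the follow-up week will be on record.
- **Use of the PP set (SAP 6.1 and 6.6.6).** Efficacy is analysed on both ITT and PP, no other population is allowed, and the primary conclusion is drawn on ITT. The primary endpoint is change in MADRS at week 6 (Visit 5). Week-7 MADRS is a secondary endpoint.

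**The concern.** A PP analysis drops patients whose data do not reflect the planned treatment. A drug first taken after the week-6 rating cannot have altered that rating, so dropping the patient does not serve that purpose. It can also do harm. A patient who has not improved by week 6 is a likely candidate to start another antidepressant once study drug has stopped, so the exclusion would depend on the outcome being analysed. PP is the plan's only alternative analysis set, and with 20 patients per arm each loss counts. At stake is how far agreement or disagreement between the PP and ITT results can be trusted.

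**Working it through.** **Step 1: dates (SAP 5.2.2 and the Part II schedule).** Dosing lasts 42 days, and Visit 6 is nominally on day 49. If study exit is Visit 6, the follow-up week is 7/49 = 14% of the medication window. With ±2 days on each visit, the gap from Visit 5 to Visit 6 runs from (49 − 2) − (42 + 2) = 3 days to (49 + 2) − (42 − 2) = 11 days.

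**Step 2: does any text stop the clock at week 6?** None was found. SAP 5.3.1 has no date and protocol 5.3 has no end. SAP 6.2.3 labels its window as treatment but runs it past the last dose. By contrast, extent of exposure in SAP 6.3.2 does end at the last drug taken, and the PP data-completeness condition is tied to the primary endpoint. SAP 6.6.9 (visit windows) and the mock-up tables were not in the text reviewed.

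**Step 3: size.** The documents give no effect size, SD or rate of new treatment, so there is no plan figure to reproduce and every input here is assumed. Let the week-6 change be normal with SD 9 and mean μ = −10 on placebo or −14 on a dose. A non-responder has a fall of less than 15 points (half of a baseline of 30). A share q of non-responders start a prohibited drug in the follow-up week.

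- Share of non-responders: p = Φ((μ + 15)/9). Placebo Φ(0.556) = 0.711; dose Φ(0.111) = 0.544.
- Share of the arm removed: q·p.
- Shift of the arm mean towards improvement: q·9·φ((μ + 15)/9) / (1 − q·p), where 9·φ = 3.077 on placebo and 3.568 on the dose.
- PP difference: 4.0 + dose shift − placebo shift.

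| q placebo / dose | Removed, placebo / dose | Shift, placebo / dose | PP difference |
|---|---|---|---|
| 10% / 10% | 7.1% / 5.4% | 0.33 / 0.38 | 4.0 |
| 30% / 30% | 21.3% / 16.3% | 1.17 / 1.28 | 4.1 |
| 20% / 10% | 14.2% / 5.4% | 0.72 / 0.38 | 3.7 |
| 50% / 30% | 35.5% / 16.3% | 2.39 / 1.28 | 2.9 |
| 30% / 50% | 21.3% / 27.2% | 1.17 / 2.45 | 5.3 |

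With no true effect (both means −10), q of 50% on placebo and 30% on the dose gives a spurious 2.39 − 1.17 = 1.2 points in favour of placebo. Swapping the rates reverses the sign.

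**Step 4: the planned test.** The primary test is Kruskal–Wallis, so mean shifts alone do not show the effect on inference. A simulation used 20 per arm and 4,000 trials per setting. It assumed baseline 30 (SD 4), change −10 on placebo and −14.5 on both doses, SD 9, and non-response as a fall of less than 50%. The start rate was equal in all arms.

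| Start rate | Mean PP size | Removed per 20, placebo / dose | Power | Rejection rate, no effect |
|---|---|---|---|---|
| 0% | 60 | 0 / 0 | 0.315 | 0.049 |
| 10% | 56.5 | 1.4 / 1.1 | 0.314 | 0.052 |
| 25% | 51.3 | 3.5 / 2.6 | 0.265 | 0.045 |
| 50% | 42.5 | 7.0 / 5.3 | 0.218 | 0.047 |

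The PP size, removals and power are for the case with a true effect. Unequal start rates were not run through the rank test.

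**The case against.** The strongest reply is that the link is inferred. SAP 6.2.3 exists to define a frequency table, and 5.3.1 does not cite it; the two share only a term. The ban in protocol 5.3 is justified by avoiding interaction with study drug, and dosing has ended by week 7. The complete-data condition hints that the PP set was meant to be anchored at week 6. Equating study exit with Visit 6 is natural, but no passage says so. All of this stands. A reader might infer that the plan definitely excludes these patients; the documents support only that its literal wording allows it. The reply does not remove the gap, because without 6.2.3 the PP rule still has no cut-off and the ban still has no end.

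A reader might also count a hypnotic started in week 7 as a clear example. It is not. Protocol 5.3 confines three named hypnotics to the period from Visit 1 to one week after Visit 2, but it refers back to the exclusion criteria, and exclusion 3 exempts insomnia treatment that the investigator judges necessary. Whether such use is permitted is unclear, and those passages must be reconciled.

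Nor do the documents show that the PP result would be biased towards the drug or its error rate inflated. At equal start rates the difference is stable and the simulated rejection rate under no effect is 0.045 to 0.052. The unequal rates are illustrations without support in the documents. Finally, the selection modelled here is on response at week 6. Selection on how patients fared after the rating is possible but was not shown.

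**Conclusion.** The point holds as a defect of wording in a supportive analysis. As written, the plan allows a drug that cannot have influenced the week-6 MADRS to remove a patient from the PP analysis of it, and that removal is plausibly related to the outcome. The reliable consequence is a smaller PP set: about 5–7% of an arm lost if 10% of non-responders start a prohibited drug, and 16–21% if 30% do. Both arm means also look better, by 1.2 to 1.3 points at 30%. The dose–placebo difference moves materially only if start rates differ by arm, and then in either direction. These sizes rest on assumed means, SD and start rates, and on study exit being Visit 6. A reader might infer that the trial's main conclusion is at risk. It is not: SAP 6.1 draws that conclusion on ITT, which this rule does not touch.

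**What to change.** Before unblinding, state in SAP 5.3.1 that, for efficacy analyses up to and including week 6, a concomitant-medication deviation counts only if the drug was taken between first dose and the Visit 5 rating. Flag later use and apply it to the week-7 PP summaries only, where it does bear on the rating. Align SAP 6.2.3, so that its label and its end date agree, and SAP 6.6.6, so that the week-7 flag is not read as an extra population.

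The cost is a few sentences across three SAP sections and one date comparison in the derivation. The downside is that PP membership can differ between week 6 and week 7, so the tables must show the number at each. No change is proposed to what patients may receive or when.

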## **6.3 Study Treatment Administration**

### **6.3.1 Treatment Compliance**

Subjects' compliance (%) during the treatment period will be tabulated by part, center, and treatment and calculated according to the following formula:

$$= 100 * \frac{\text{Number of study medication actually took during the extent of exposure}}{\text{Number of study medication should be taken during the extent of exposure (#)}}$$

# = (number of study medication should be taken per day) \* (extent of exposure, section 6.3.2)

### **6.3.2 Extent of Exposure**

Extent of exposure (days) = date of last drug taken – date of first drug taken + 1

If the date of first drug taken is not available, the date when the drug was firstly dispensed will be used for calculation.

If the date of last drug taken is not available, the date will be replaced with that of the last drug return, previous drug taken, or previous drug return in order.

### **6.3.3 Mean Daily Dose**

Descriptive statistics of mean daily dose of the test drug will be presented by part, center, and treatment.

$$\text{Mean daily dose} = \frac{\text{Number of study medication taken}}{\text{Extent of exposure (section 6.3.2)}}$$

## 6.4 Analysis of Efficacy

Results of efficacy will be presented with descriptive statistics (i.e. sample size, number of missing data, mean, 95% confidence interval of mean, median, standard deviation, inter-quartile range, maximum and minimum) for continuous parameters by part, visit, and treatment. Line charts of all efficacy outcomes will be generated and presented as mean and standard deviation.

### 6.4.1 Primary Efficacy Endpoint

In part II study, the primary endpoint is the net change of the MADRS total score at the 6th week after treatment (Mean MADRS total score at week 6 – Mean MADRS total score at baseline [Visit 2]).

Kruskal-Wallis test will be implemented to test the group difference.

The primary hypothesis will be:

$$\begin{aligned}
 H_0: & \text{The mean ranks of the groups are the same} \\
 H_a: & \text{The mean ranks of the groups are not the same}
 \end{aligned}$$

One a significant treatment effect is found, Wilcoxon rank sum test with Holm procedure will then be performed for comparisons between two treatment groups and the placebo group. The treatment group will be declared superior if null hypothesis is rejected and  $\mu_{t1}$  and/or  $\mu_{t2}$  is greater than  $\mu_p$ .

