Based on the results, the maximum tolerated dose (MTD) is ≥ 3800 mg of PDC-1421 Capsule so that the safe and well-tolerated for PDC1-421 Capsule is from 380 mg to 3800 mg. According to studies in mouse model system to evaluate efficacious dose, TBZ-induced hypothermia assay, PDC-1421 was indicated to be efficient at 100 mg/kg and 300 mg/kg doses which are equivalent to about 480 mg and 1400 mg in human subjects. We choose 1140 mg (3 capsules), between the efficient dosage, and 2280 mg (6 capsules), above the efficient dosage, which is based on the mice study as the dosage regimen of Phase II trial.

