## 5. INVESTIGATIONAL PLAN

### 5.1 Objective

#### 5.1.1 *Primary objective*

The primary objective of this trial was to determine the effective doses and treatment period of PDC-1421 Capsule in subjects with MDD.

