### 5.2 Study Design

The screening phase is intended for diagnosing and assessing the patient for possible inclusion in the study and for providing an adequate washout period. The following study will be conducted in two parts. The targeted population of this study is 72 subjects who met the intent-to-treat (ITT) basis, in which 12 are assigned to part I, 60 are assigned to part II. Part I is an open-label study, multiple center and dose escalation evaluation in twelve patients. Six subjects each will be evaluated for any safety concerns at 1 or 2 capsules TID dose for 28 days, sequentially. Each of them will be assessed twice in the first week after administration of PDC-1421 Capsules and once a week in the following treatment. Part II is a randomized, double-blind, placebo-controlled, parallel-group study. 60 subjects will be randomly assigned on a 1:1:1 basis to one of the three treatment arms (1 PDC-1421 Capsule plus 1 placebo TID, 2 PDC-1421 Capsule TID, 2 placebo TID) for 6 weeks (42 days) and evaluated the safety and efficacy every two weeks during the treatment period. The performance of PDC-1421 Capsule on MDD subjects will provide us with valuable information for our next phase of the study.

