**5.3.3 Statistical Evaluation**

Simple descriptive statistics with 95% confidence interval will be performed with data collected in this study wherever applicable. Treatment effects are evaluated based on 2-sided test with a 0.05 significant level. All data shall be tabulated and presented in the study report. The descriptive statistics will be provided. The safety and efficacy data will be analyzed using the non-parametric method.

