### ***6.6.5 Multiple Comparisons / Multiplicity***

The Holm procedure will be carried out for the post-hoc test of the primary endpoint.

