## 7. DOCUMENTATION OF STATISTICAL METHODS

### 7.1 Documentation of Statistical Methods

Following SAS procedures will be applied for statistical methods mentioned in Chapter 6.

SAS procedure	Statistical Analysis Method	Comment
Freq	Frequency table	
	Cochran-Mantel-Haenszel Test	Test of association between variables by controlling for multiple centers
Sgplot	Graph	
NPAR1WAY	Kruskal-Wallis test	To test group difference of continuous variables
	Wilcoxon rank sum test	Post-hoc test
MULTTEST	Holm's Procedure	Significant level control for Multiplicity
MEANS	Descriptive Statistics	Means, SD, Min, Max, Med, IQR, P1, P3

\*Center effect will be incorporated in only when degree of freedom is sufficient.

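### SAP 6.4.1 controls familywise error but is stricter than three arms require: after the Kruskal-Wallis gate, Holm costs about 1-2 points of power if both doses work and about 4-7 if only one does

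*SAP*

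**What the plan says.** SAP 6.4.1 sets a two-stage test for Part II. At the first stage, "Kruskal-Wallis test will be implemented to test the group difference". Once that is significant, "Wilcoxon rank sum test with Holm procedure will then be performed for comparisons between two treatment groups and the placebo group". SAP 6.6.5 repeats the adjustment: "The Holm procedure will be carried out for the post-hoc test of the primary endpoint". The MULTTEST row of the table in SAP 7.1 gives its purpose as "Significant level control for Multiplicity".

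The level comes from SAP 5.3.3: "Treatment effects are evaluated based on 2-sided test with a 0.05 significant level". The size comes from SAP 5.2: "60 subjects will be randomly assigned on a 1:1:1 basis to one of the three treatment arms". Neither SAP 5.3.4 nor Protocol 8.1 gives an effect size, a standard deviation or a power for the 60 subjects. No reason is given for using both a gate and Holm.

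**The concern.** The gate and Holm each protect against a false dose claim. With two comparisons against placebo in a three-arm trial, the gate leaves nothing for Holm to protect, so Holm only raises the bar for naming a dose.

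What is at stake is power and a clear answer. SAP 5.1.1 states the aim: "The primary objective of this trial was to determine the effective doses and treatment period of PDC-1421 Capsule in subjects with MDD". With 20 per arm, one unhelpful result is a significant Kruskal-Wallis test after which neither dose can be named. Holm makes that result more frequent.

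**Working it through.** **Inputs from the documents.** Three arms, 60/3 = 20 per arm (SAP 5.2); two-sided 0.05 (SAP 5.3.3); Kruskal-Wallis, then two Wilcoxon tests against placebo with Holm (SAP 6.4.1). The plan states no power or familywise error, so there is no figure to reproduce.

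**Step 1: the rules as p-value conditions.** Let p_KW be the Kruskal-Wallis p-value, and p_min and p_max the smaller and larger Wilcoxon p-values.

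- SAP rule: at least one claim if p_KW ≤ 0.05 and p_min ≤ 0.05/2 = 0.025; both doses if also p_max ≤ 0.05.
- Gate without Holm: given p_KW ≤ 0.05, each dose is claimed if its own p ≤ 0.05.
- Holm without the gate: at least one claim if p_min ≤ 0.025; both if also p_max ≤ 0.05.

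Every rejection by the SAP rule is also a rejection by each of the other two. Neither can have less power than the SAP rule; only the size of the gain needs simulation.

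**Step 2: familywise error of the gate without Holm.** Take each null to be equality of distributions.

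- Both dose-placebo nulls true: all three arms are equal, and any claim needs p_KW ≤ 0.05, so the error is at most 5%.
- One null true: the only possible false claim needs that comparison's Wilcoxon p ≤ 0.05, so the error is at most 5%.

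These are all the cases, so the rule is a closed test.

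**Step 3: simulated error.** 100,000 trials per scenario, 20 per arm, normal change scores with SD 10 rounded to integers, tie-corrected Kruskal-Wallis (chi-square, 2 df), Wilcoxon with continuity correction.

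- All arms equal, any false claim: SAP rule 3.4%, gate without Holm 4.0%, Holm without gate 4.4%. A separate run of 200,000 trials gave about 8.9% with neither protection, so the gate does the necessary work.
- Only the high dose active, false low-dose claim with the gate alone: at most 4.8%. In the 200,000-trial run it reached at most 5.0%, with the active dose as far out as 3 SD.
- Equal centres, unequal spread (placebo/low/high SD 10/10/14, 14/10/10, 7/10/13), any false claim with the gate alone: 4.2%, 4.3%, 4.4%.

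**Step 4: simulated power.** The effects are assumptions, in SD units for low/high dose.

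| Scenario | SAP rule | Gate, no Holm | Gain (points) | Holm, no gate |
|---|---|---|---|---|
| Both active, at least one claim: 0.5/0.5 | 30.0% | 31.3% | 1.3 | 33.6% |
| 0.3/0.6 | 30.7% | 32.8% | 2.1 | 34.3% |
| 0.4/0.8 | 52.9% | 55.0% | 2.1 | 56.7% |
| 0.6/0.8 | 58.4% | 59.8% | 1.4 | 62.1% |
| 0.8/0.8 | 68.2% | 69.5% | 1.3 | 71.3% |
| 1.0/1.0 | 87.1% | 87.9% | 0.8 | 88.7% |
| Only high dose active, high dose detected: 0/0.5 | 20.1% | 23.9% | 3.8 | 21.9% |
| 0/0.8 | 53.3% | 60.2% | 6.9 | 54.8% |
| 0/1.0 | 75.4% | 81.5% | 6.1 | 76.2% |

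Claims for both doses gain less: 18.8% to 19.2% at 0.4/0.8, and 49.8% to 50.8% at 0.8/0.8.

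**Step 5: gate significant but no dose named** (SAP rule against gate without Holm): 1.7% against 0.2% at 0.6/0.8; 3.0% against 0.9% at 0.4/0.8; 15.4% against 7.7% at 0/0.8.

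**Step 6: robustness** (60,000 trials each). At 0.6/0.8, at least one claim, SAP rule / gate without Holm / Holm without gate:

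- 16 per arm: 46.8 / 48.6 / 50.9%
- t with 4 df: 74.1 / 75.5 / 77.0%
- skewed gamma: 72.1 / 73.9 / 73.6%

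With only the high dose active at 0.8 SD, detection rises from 41.8% to 48.3%, 70.0% to 76.4% and 69.0% to 75.9% in the same three settings.

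**The case against.** The strongest reply is that nothing is broken. Gate plus Holm is pre-specified, is consistent across SAP 6.4.1, 6.6.5 and 7.1, and controls familywise error. SAP 6.4.2 runs the secondary post-hoc tests without Holm, so the stricter rule may be a deliberate choice for the primary claim. If both doses work, the gain is only 1-2 points. That stands, and it is why this is an option and not a correction. It does not give Holm a purpose: SAP 7.1 says that it is there for multiplicity, and the gate already provides that.

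A second reply is that, if both doses work, the gate costs more than Holm does. This also stands for normal data: Holm without the gate gains a further 0.8 to 2.3 points over the gate without Holm. If only one dose works the order reverses (54.8% against 60.2% at 0.8 SD), and with skewed data and both doses active the advantage disappears. Dropping the gate would also change the primary hypothesis stated in 6.4.1.

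A third reply is timing. SAP version 01 was approved in June 2019 (SAP 11.4), and SAP 6.6.4 speaks of the trial's conduct in the past tense. Relaxing a primary rule late invites challenge. The documents give no unblinding date, so this makes the change conditional but does not rule it out.

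**Conclusion.** SAP 6.4.1 holds familywise error at 5% and is somewhat more conservative than three arms need. Dropping Holm and keeping the gate gains about 1-2 points for at least one dose claim if both doses work, and about 4-7 points for the active dose if only one does. That the new rule holds 5% and never loses power follows from the logic. The sizes rest on assumed effects of 0.3 to 1.0 SD, mainly normal data, and 20 per arm.

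A reader might infer three stronger things that the documents do not support.

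- *That only the 1-2 point figure matters because both doses are expected to work.* Protocol 1.5 says "We choose 1140 mg (3 capsules), between the efficient dosage, and 2280 mg (6 capsules), above the efficient dosage", but this explains a dose choice from a mouse assay. It is not a forecast for patients, so both scenarios belong in the conclusion.
- *That 6.4.1 is sound as a whole.* Only familywise error is examined here. The section takes change as week 6 minus baseline and declares superiority when the treatment mean exceeds placebo, whereas Protocol 6.2 makes higher MADRS scores worse. That is a separate problem and is not endorsed.
- *That using Holm is an error.* It is a valid, pre-specified choice that costs some power.

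**What to change.** Only if the sponsor confirms that treatment codes are still closed: in SAP 6.4.1, replace the Holm-adjusted post-hoc step with *Wilcoxon rank sum tests, each at two-sided 0.05, performed only if the Kruskal-Wallis test is significant*. Align 6.6.5 and the MULTTEST row in 7.1. State that control rests on closed testing for pairwise comparisons among exactly three arms on one primary endpoint, and would not carry over to a fourth arm or a further primary endpoint. A high-against-low comparison on the same endpoint would remain covered: any of the three claims with all arms equal occurred in 4.9% of simulated trials.

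The cost is wording in three places and a rise in error with all arms equal from about 3.4% to about 4.0%. The primary hypothesis, 5% level, sample size and data collection do not change. If the codes are already open, leave the rule as it is.
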